20.8 Case definitions of probable and confirmed myocarditis, pericarditis, and myopericarditis

Condition	Definition	
Acute myocarditis	Probable case 
 Presence of ≥1 new or worsening of the following clinical symptoms:* • chest pain, pressure, or discomfort • dyspnea, shortness of breath, or pain with breathing • palpitations • syncope 
OR, infants and children aged <12 years might instead have ≥2 of the following symptoms:
 
 • irritability • vomiting • poor feeding • tachypnea • lethargy 
AND
 
≥1 new finding of
 
 • troponin level above upper limit of normal (any type of troponin) • abnormal electrocardiogram (ECG or EKG) or rhythm monitoring findings consistent with myocarditis[§] • abnormal cardiac function or wall motion abnormalities on echocardiogram • cMRI findings consistent with myocarditis[¶] 
AND
 
 • No other identifiable cause of the symptoms and findings 	Confirmed case 
 Presence of ≥1 new or worsening of the following clinical symptoms:* • chest pain, pressure, or discomfort • dyspnea, shortness of breath, or pain with breathing • palpitations • syncope 
OR, infants and children aged <12 years might instead have ≥2 of the following symptoms:
 
 • irritability • vomiting • poor feeding • tachypnea • lethargy 
AND
 
≥1 new finding of
 
 • Histopathologic confirmation of myocarditis[†] • cMRI findings consistent with myocarditis[¶] in the presence of troponin level above upper limit of normal (any type of troponin) 
AND
 
 • No other identifiable cause of the symptoms and findings
Acute pericarditis**	Presence of ≥2 new or worsening of the following clinical features: 
 • acute chest pain^{††} • pericardial rub on exam 	

Condition	Definition
	
 • new ST-elevation or PR-depression on EKG • new or worsening pericardial effusion on echocardiogram or MRI
Myopericarditis	This term may be used for patients who meet criteria for both myocarditis and pericarditis.

Abbreviations: AV = atrioventricular; cMRI = cardiac magnetic resonance imaging; ECG or EKG = electrocardiogram.

* Persons who lack the listed symptoms but who meet other criteria may be classified as subclinical myocarditis (probable or confirmed).

[†] Using the Dallas criteria (Aretz HT, Billingham ME, Edwards WD, et al. Myocarditis. A histopathologic definition and classification. Am J Cardiovasc Pathol 1987; 1:3–14). Autopsy cases may be classified as confirmed clinical myocarditis on the basis of meeting histopathologic criteria if no other identifiable cause.

[§] To meet the ECG or rhythm monitoring criterion, a probable case must include at least one of 1) ST-segment or T-wave abnormalities; 2) Paroxysmal or sustained atrial, supraventricular, or ventricular arrhythmias; or 3) AV nodal conduction delays or intraventricular conduction defects.

[¶] Using either the original or the revised Lake Louise criteria. <https://www.sciencedirect.com/science/article/pii/S0735109718388430?via%3Dihub>

^{**} <https://academic.oup.com/eurheartj/article/36/42/2921/2293375>

^{††} Typically described as pain made worse by lying down, deep inspiration, or cough, and relieved by sitting up or leaning forward, although other types of chest pain might occur.

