8.1.3 Baseline (Week 0/Day 1) Visit

Eligible participants who meet all inclusion criteria and none of the exclusion criteria will proceed with visits and assessments according to Section 20.1 Schedule of Events. Eligible participants will be assessed for disease activity and SARS-CoV-2 infection at the Baseline/Week 0 visit, prior to receipt of an additional homologous vaccine dose. Prior to administering the additional homologous vaccine dose at the Baseline visit, the site will confirm the participant meets vaccine eligibility per the criteria below:

- No increase to the permitted concomitant medications in participants in Cohorts A and B between Randomization and Baseline/Week 0.
- No B-cell depletion infusions or changes in permitted concomitant medications in participants in Cohort C between allocation and Baseline/Week 0.
- No clinically active disease (including myocarditis or pericarditis) at Baseline/Week 0 resulting in an increase/addition of IS medications. For participants with MS, no suggestion of a MS relapse per the investigator.
- No active myocarditis or pericarditis based on review of clinical symptoms.
- No positive molecular COVID-19 test at Baseline/Week 0.
- No increase in oral, intramuscular, or intravenous steroids within 14 days of Baseline/Week 0.

If the vaccine cannot be administered at the Baseline/Week 0 visit, it must be administered during the following 2-3 days. Vaccine eligibility will be confirmed prior to administration of the vaccine. **Administration of the additional homologous vaccine dose must occur within 28 days of the Screening visit.**

If a participant is not eligible to receive the additional homologous vaccine dose at Baseline/Week 0, he/she will be terminated from the study. The participant may rescreen under a new participant ID after 30 days from the determination of vaccine ineligibility. Participants who were randomized to withhold cohort-defining IS medications before the Baseline visit and who are not eligible to receive an additional homologous vaccine dose at that visit, may restart their IS medications immediately. The participant will be replaced.

See Section 8.1.4 Study Procedures and Assessments for more information on individual clinical and research assessments.

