12.2.5 Adverse Events of Special Interest

Adverse events of special interest (AESIs) include the following:

- Myocarditis (probable and confirmed cases)
- Pericarditis

See Appendix 20.8 for cases definitions of probable and confirmed myocarditis and pericarditis according to the Centers for Disease Control and Prevention (CDC) criteria

In addition, the following AESI will be collected in the arms in which the Sanofi-GSK COVID-19 Vaccine is administered.

- New onset of potential immune-mediated diseases (pIMDs).

See Appendix 20.7. Disease flares of the underlying autoimmune disease, including new manifestation of the disease will not be captured as an AESIs. Disease flares should be reported following Section 12.4.2 Increase in Autoimmune Disease Activity.

pIMDs are a subset of AEs that include autoimmune diseases and other inflammatory and/or neurologic disorders of interest which may or may not have an autoimmune etiology. AEs that need to be recorded and reported as pIMDs, including those listed in Appendix 20.7.

However, the Investigator will exercise their medical and scientific judgment in deciding whether other diseases have an autoimmune origin (that is pathophysiology involving systemic or organ-specific pathogenic autoantibodies) and should also be recorded as a pIMD. When there is enough evidence to make any of the diagnoses mentioned in Appendix 20.7 the AE must be reported as a pIMD. Symptoms, signs or conditions which might (or might not) represent the above diagnoses, should be recorded and reported as AEs but not as pIMDs until the final or definitive diagnosis has been determined, and alternative diagnoses have been eliminated or shown to be less likely.

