12.4 Collection and Recording of Adverse Events

12.4.1 Collection Period For All Cohorts

For this study, the timelines below apply after each study-administered vaccine:

- Solicited AEs (all grades) will be collected from Day 1 (vaccine administration) through 7 days post study vaccination.
- Unsolicited AEs will be collected as follows:
 - Any unsolicited AEs that are Grade 3 or higher will be collected from randomization/allocation through vaccination administration.
 - All unsolicited AEs (all grades) will be collected from Day 1 through Day 28.

- Any flares of a secondary autoimmune disease will be reported as an unsolicited AE (all grades) and will be collected from Day 1 through the end of the participant's study participation.
- AESIs will be collected as follows:
 - Pericarditis/myocarditis events will be collected in all treatment arms. NCI-CTCAE Grade 2 or higher myocarditis and pericarditis events from Day 1 through the end of the participant's study participation.
 - New onset of pIMDs will only be collected in arms where the Sanofi-GSK COVID-19 Vaccine is administered. All grades will be collected from Day 1 through the end of the participant's study participation.
- SAEs, MAAEs, and NOCMCs will be collected from Day 1 through the end of the participant's study participation, regardless of NCI-CTCAE grade.
- COVID-19 diagnoses (all grades) confirmed by molecular COVID-19 testing will be collected from Day 1 through the end of the participant's study participation.

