12.4.2 Increase in Autoimmune Disease Activity

Any increase in autoimmune disease activity (flare/relapse) for the participant's qualifying autoimmune disease will not be reported as an AE. These events will be collected and reported on the disease-specific assessment eCRFs. (Section 8.1.4.2 Disease-Specific Assessments).

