12.8.2.2 Ad hoc DSMB Reviews

12.8.2.2.1 Ad Hoc DSMB Reviews for Adult Participants

In addition to the pre-scheduled data reviews and planned safety monitoring, the DSMB may be called upon for ad hoc reviews. The DSMB will review any event that potentially impacts safety at the request of the protocol chair or DAIT/NIAID. Any of the following events will trigger an ad hoc DSMB Safety Review:

- Death related to vaccine
- Life-threatening AE (Grade 4) related to vaccine
- Permanent or severe disability related to vaccine
- Occurrence of a Grade 3 or higher, vaccine-related SAE of the same type in 3 or more of the study participants who have received a study treatment. *Note: Only SAEs occurring within 24 weeks of a Day 1 visit will be counted.*
- Occurrence of a Grade 2 or higher myocarditis or pericarditis within 6 weeks of vaccine administration. *Note: the DSMB chair will be notified within 3 business days from when the AESI is reported to DAIT/NIAID.*
- Occurrence of severe flare or relapse after an additional homologous COVID-19 vaccine dose given at Stage 1, defined as within 12 weeks of the Stage 1 Baseline/Week 0 visit (vaccination), in 3 of the first 10 participants or 30% thereafter, defined as follows.
- Occurrence of severe flare or relapse after a subsequent alternative COVID-19 vaccine dose given at Stage 2, defined as within 12 weeks of the Stage 2 Baseline/Week 0 visit (vaccination), in 3 of the first 10 participants or 30% thereafter.

Severe flare or relapse is defined as follows:

- **RA:** DAS28-CRP score >5.1.
- **SLE:** Severe score on the SELENA-SLEDAI flare index.
- **SSc:** Onset of new or significant worsening of internal organ involvement requiring hospitalization or change in treatment or worsening of skin thickening on the modified Rodnan skin score of >4 units [absolute change from screening visit].
- **MS:** Clinical relapse meeting either the criteria specified in (a) with investigator determination of relapse or the criteria in (a) **and** (b) below:

- a. Occurrence of new, recurrent or worsening neurological symptoms attributable to MS, that meet all of the following criteria:
 - i. Appeared or evolved subacutely (over <3 months).
 - ii. Persisting for >24 hours.
 - iii. Cannot be attributed to confounding factors (e.g., fever, infection, injury, poor sleep, adverse reaction to medication).
 - iv. Occur ≥ 30 days after the onset of a prior confirmed relapse.

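### The protocol conflicts on whether Grade 2 or higher myocarditis or pericarditis within 6 weeks of a study vaccine is reported as an AESI when the site attributes it to the autoimmune disease

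*Protocol*

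**What the plan says.** **Text with no condition on cause**
- Protocol 12.4.1: "Pericarditis/myocarditis events will be collected in all treatment arms", at Grade 2 or higher, from Day 1 to the end of participation.
- Protocol 12.8.2.2.1, with the same item for children in 12.8.2.2.2, lists as an ad hoc trigger: "Occurrence of a Grade 2 or higher myocarditis or pericarditis within 6 weeks of vaccine administration".
- Protocol 11.5: for any such event the DSMB chair is told within 3 business days of the AESI report to the sponsor, and decides whether the full board meets.
- Protocol 12.5.2: sites report AESIs within 24 hours whatever the relationship to vaccine.

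**Text that makes cause matter**
- Protocol 12.2.5 lists as an AESI "Myocarditis (probable and confirmed cases"), and refers to Appendix 20.8 for the definitions.
- Appendix 20.8 requires, for probable and for confirmed myocarditis alike, "No other identifiable cause of the symptoms and findings". The acute pericarditis row asks for "Presence of ≥2 new or worsening of the following clinical features" and has no clause on cause.
- Protocol 12.4.2: increased activity of the "qualifying autoimmune disease will not be reported as an AE". It goes on the disease-specific forms.
- Protocol 12.2.5 also says: "Disease flares of the underlying autoimmune disease, including new manifestation of the disease will not be captured as an AESIs". This sentence follows the text on potential immune-mediated diseases (pIMDs), which are collected only in the Sanofi-GSK arms.
- The synopsis (Study Stopping Rules) heads the adult and pediatric trigger lists as events attributed to the vaccine.

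**The concern.** Section 5.1.1 names myocarditis and pericarditis as known reactions to both mRNA vaccines, and the trial sets a one-event notice for them. In these participants the same condition can also be read as disease activity. The vaccination criteria in Section 8.1.3 do so themselves: "No clinically active disease (including myocarditis or pericarditis) at Baseline/Week 0". Many participants also withhold MMF/MPA or MTX around the dose (Section 7.1.1), and Section 5.3.1 warns that this may cause a flare. A flare explanation is thus available in the very weeks when the vaccine signal is sought.

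If the site's view of cause decides whether an AESI report is made, it also decides whether the DSMB chair hears of the event promptly. The AESI count would then depend on each site's habits of attribution.

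**Working it through.** The documents state no figure for this trigger, so the main check is to follow one event through the text. Take a Grade 2 event two weeks after the dose that the site ascribes to the qualifying disease.

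| Event | 20.8 definition | Flare rules | 12.4.1, 11.5, 12.8.2.2 |
|---|---|---|---|
| Myocarditis, mRNA arm | Fails the cause element, so not a probable or confirmed case | 12.4.2: not an AE | Collect and notify |
| Pericarditis, mRNA arm | Met; no cause element | 12.4.2: not an AE; reach of 12.2.5 arguable | Collect and notify |
| Either, Sanofi-GSK arm | As above | 12.4.2, and 12.2.5 more directly, since the pIMD list in Appendix 20.7 names immune-mediated myocarditis and pericarditis | Collect and notify |

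Every row yields two answers, and no passage gives precedence.

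**Do other provisions close the gap?**
- The 24-hour rule in 12.5.2 ignores relationship, but only for events already classed as SAEs or AESIs.
- The Medical Monitor's final say on attribution (12.3.2) covers adverse events; 12.4.2 says a flare is not reported as one.
- An admitted case might be an SAE, but 12.2.6 defines an SAE as a kind of adverse event or suspected reaction, so the same conflict returns.
- Medically attended events (12.2.4) must be possibly related or related to vaccine, which again turns on attribution.
- The chair's clock in 11.5 and 12.8.2.2 starts at the AESI report. Without a report it does not start.
- The SAP, written to protocol version 3.0, has no AESI category and does not settle the matter.

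**Can the severe-flare rule stand in?** It needs 3 of the first 10 participants, or 30% thereafter. For illustration take n = 80, the Adult Stage 2 maximum per arm (Section 3.1.1.2), where 30% is 0.30 × 80 = 24. True event rates p of 0.5%, 1% and 2% are assumptions, because the documents give none.

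- At least one event in 80: 1 − (1 − p)^80.
- At least 3 in the first 10: the sum over k = 3 to 10 of C(10,k) p^k (1 − p)^(10−k).
- At least 24 in 80: the same binomial tail with n = 80.

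| p | At least 1 of 80 | At least 3 of 10 | At least 24 of 80 |
|---|---|---|---|
| 0.5% | 0.33 | 0.00001 | effectively 0 |
| 1% | 0.55 | 0.0001 | effectively 0 |
| 2% | 0.80 | 0.0009 | effectively 0 |

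The last two columns count these events alone; in practice they would add to other severe flares. Even then they must meet the severe-flare definition. For RA, MS, pemphigus and JIA, Section 12.8.2.2 builds that on joint, neurological or skin findings with no cardiac item. For SSc it does include internal organ involvement. The flare rule is no substitute for a one-event notice.

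**The case against.** The best defence is that the specific rules govern. Sections 11.5, 12.4.1 and 12.8.2.2 speak of any Grade 2 or higher event and attach no test of cause, while the flare wording is general and, in 12.2.5, sits in pIMD text for one vaccine. That is a fair reading, and it means the events are not cleanly excluded. But no passage says so, and 12.4.2 applies to all arms.

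The vaccination criteria are also weak evidence. They are not a reporting rule, and a separate item in the same list bars active myocarditis or pericarditis without regard to cause. They show only that the flare reading is one the protocol admits.

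The events would not be invisible. Shortness of breath and, from age 5, chest pain are solicited for 7 days (12.2.1.3) and are attributed to vaccine by rule (12.3.2). If ongoing at Day 7 they are entered and followed (12.5.1). Section 5.1.1 says onset is usually within days and requires cardiology referral for suggestive symptoms. Flares are in the planned DSMB data, and the medical monitor or co-chairs may ask for a review (12.8.2.1). This gives partial visibility. It does not produce an AESI report: the diary records symptoms rather than diagnoses and covers 7 of the 42 days in the window, and planned reviews come about every 6 months.

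The scope is narrower than the whole trial, too. A cardiac flare is a less natural reading in diseases whose flare definitions are joint, neurological or skin based.

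**Conclusion.** The conflict is real and should be resolved. Myocarditis can be kept out of AESI reporting by two routes, the cause element of 20.8 and the flare rule in 12.4.2. Pericarditis can be kept out only by the flare rules, and the reach of the 12.2.5 sentence to the mRNA arms is arguable.

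A reader might infer three stronger things that the documents do not support:
- That the protocol removes these events. It gives contradictory instructions, some of which require the report.
- That one event forces a full DSMB review. Section 11.5 makes it a notice to the chair, who decides; the trigger lists read as though the review were automatic, which is itself a point to reconcile.
- That some given share of events will be missed. The documents offer no event rate and no attribution share.

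The size is therefore stated per event: one case entered only as a flare is enough to lose its own prompt notice to the chair. This assumes that some sites will follow the flare rule or the cause element rather than 12.4.1. The probabilities above show only that the flare rule cannot replace the one-event notice; they do not estimate how often events would be lost.

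**What to change.** Reconcile the synopsis stopping rules with Sections 11.5, 12.2.5, 12.4.1, 12.4.2, 12.8.2.2.1, 12.8.2.2.2 and Appendix 20.8, as follows.

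1. State in 12.2.5 and 12.4.2 that the flare exclusion does not apply to Grade 2 or higher myocarditis or pericarditis within 6 weeks of a study vaccine.
2. Require such events that meet the symptom and objective-finding elements of 20.8 to be reported as AESIs within the existing 24 hours and notified to the DSMB chair, whatever the site's attribution.
3. Record attribution (vaccine, disease, other) in a separate field that the chair can see.
4. Leave the 20.8 definitions unchanged for classifying cases, so that comparability with the CDC criteria is kept.
5. Align the synopsis heading with 12.8.2.2, and say in one place what a single event sets in motion.
6. Continue the disease-specific flare forms in parallel.

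The cost is protocol and eCRF-guidance wording. The downside is that some events due to the autoimmune disease will be sent to the chair.

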1. LIST OF ABBREVIATIONS

Table 1: List of Abbreviations

Abbreviation	Term
ACE	Autoimmunity Centers of Excellence
AE	Adverse event
CRF	Case report forms
CSR	Clinical Study Report
CV	Coefficient of variation
DAIT	Division of Allergy, Immunology, and Transplantation
DAS	Disease Activity Score
DAS28-CRP	Disease Activity Score 28 using C-reactive protein
DSMB	Data and Safety Monitoring Board
EDSS	Expanded Disability Status Scale
H-SLEDAI	Hybrid Systemic Lupus Erythematosus Disease Activity Index
IS	Immunosuppressive medications
JADAS	Juvenile Arthritis Disease Activity Score
JDM	juvenile dermatomyositis
JIA	juvenile idiopathic arthritis
LLOD	Lower Limit of Detection
MAAE	medically attended adverse event
MCAR	Missing-completely-at-random
MedDRA	Medical Dictionary for Regulatory Activities
MMF	Mycophenolate mofetil
MPA	Mycophenolic acid
MS	Multiple sclerosis
MTX	Methotrexate
NCI	National Cancer Institute
NIAID	The National Institute of Allergy and Infectious Diseases
NIH	National Institutes of Health
NOCMC	New onset chronic medical condition
PASI	Psoriasis Area and Severity Index

The National Institute of Allergy and Infectious Diseases (NIAID)
Statistical Analysis Plan - Protocol ACV01

PDAI	Pemphigus Disease Area Index
PedsQL	Pediatric Quality of Life Inventory™
PGI-C	Patient Global Impression of Change
PtGA	Patient's Global Assessment
PGA	Physician Global Assessment
POMS	Pediatric-onset multiple sclerosis
PROMIS	Participant-Reported Outcomes Measurement Information System
PT	Preferred term
RA	Rheumatoid arthritis
RBD	Receptor binding domain
SACCC	Statistical and Clinical Coordinating Center
SAE	serious adverse event
SAP	Statistical analysis plan
SARS-COV-2	Severe Acute Respiratory Syndrome Coronavirus-2
SD	Standard deviation
SARS-COV-2	Severe Acute Respiratory Syndrome Coronavirus-2
SELENA-SLEDAI	Safety of Estrogens in Lupus Erythematosus: National Assessment– Systemic Lupus Erythematosus Disease Activity Index
SLE	Systemic lupus erythematosus
SOC	System organ class
SSc	Systemic sclerosis
VRC	Vaccine Research Center
WHO	World Health Organization

2. PURPOSE OF THE ANALYSES

The purpose of this statistical analysis plan (SAP) is to describe the planned analyses and data displays to be included in the Clinical Study Report (CSR) for Protocol ACV01. This document provides details on study populations, how the variables will be derived, how missing data will be handled and details on statistical methods to be used to analyze the safety and efficacy data.

The SAP is based on ICH guidelines E3 and E9 (Statistical Principles for Clinical Trials).

The document will be updated over time to reflect the requirements of the adaptive study design, protocol amendments and any regulatory requests. However, the final SAP must be finalized, approved by the Client, and placed on file before database is locked. If differences occur between analyses described in the SAP and the current protocol, those found in this SAP will assume primacy. Deviations from the final approved plan will be noted in the clinical study report.

3. PROTOCOL SUMMARY

Version 1.0 of the protocol was finalized July 9, 2021; the protocol is currently under Version 3.0 which includes several of the planned adaptive elements to ACV01, and is summarized below.

Title	Booster effects with autoimmune treatments in patients with poor response to initial COVID-19 vaccine
Short Title	COVID-19 BOOSTER VACCINE IN AUTOIMMUNE DISEASE NON-RESPONDERS
Clinical Phase	II
Number of Sites	Adult population: 15 – 20 sites in the United States (US) that are active National Institute of Allergy and Infectious Diseases (NIAID) Autoimmunity Centers of Excellence (ACE) or active subaward recipients of the NIAID ACE Network Pediatric population: 15 – 20 sites in the US.
IND Sponsor/Number	The National Institute of Allergy and Infectious Diseases (NIAID) / IND #27528
Study Objectives	
Hypotheses
 
• We hypothesize that adult and pediatric participants with autoimmune diseases requiring immunosuppressive (IS) medications who have had a sub-optimal response to an initial COVID-19 vaccine regimen may demonstrate enhanced immune response after receiving an additional homologous dose of an mRNA or vector-based vaccine.• We hypothesize that adult and pediatric participants with transient cessation of mycophenolate mofetil (MMF)/ mycophenolic acid (MPA) or methotrexate (MTX) before and after vaccination will have an enhanced immune response.• We further hypothesize that adult participants with autoimmune diseases requiring IS medications who continue to have a sub-optimal response after an initial COVID-19 vaccine regimen plus an additional homologous vaccine dose may demonstrate enhanced immune response after receiving an additional dose of an alternative COVID-19 vaccine. 
Primary Objective The primary objective is to determine the proportions of adult and pediatric participants who have a protective antibody response at 4 weeks after an additional homologous dose of a COVID-19 vaccine using the NIAID Vaccine Research Center (NIAID-VRC) MSD 3 plex (Wu-1 full-length spike, RBD, and N proteins) assay within arms defined by the initial COVID-19 vaccine regimen received, IS regimens, and treatment plans to either withhold or continue medications around the time of vaccination.
 
Secondary Objectives Stage 1 Secondary Objectives (adult & pediatric):

- To determine the incidence of seroconversion following an additional homologous COVID-19 vaccine dose in the subgroup of participants that are anti-COVID-19 antibody negative at Baseline.
- To determine the incidence of adverse events (AEs), including medically attended adverse events (MAAEs), new onset chronic medical conditions (NOCMCs), and serious adverse events (SAEs) following an additional homologous COVID-19 vaccine dose.
- To assess whether responses to an additional homologous COVID-19 vaccine dose differ with temporary cessation of IS medications around the time of vaccine.
- To assess whether responses to an additional homologous COVID-19 vaccine dose differ by type of vaccine administered.
- To assess whether responses to an additional homologous COVID-19 vaccine dose differ by type of cohort-defining IS medications and by disease type.
- To assess whether response to an additional homologous COVID-19 vaccine dose is associated with corticosteroid dose at the time of vaccination.
- To assess whether response to an additional homologous COVID-19 vaccine dose is associated with clinical parameters including disease activity, co-morbid illness, age, and sex.
- To determine whether disease activity is increased following an additional homologous COVID-19 vaccine dose, and if so, whether Baseline or induced immunologic variables are associated with increased disease activity and/or vaccination response.

Stage 2 Secondary Objectives (adult):

- To determine the proportions of participants with a negative serologic or sub-optimal response to an additional homologous COVID-19 vaccine dose who develop a protective antibody response after receiving a subsequent alternative vaccine dose, evaluated using the NIAID-VRC MSD 3 plex (Wu-1 full-length spike, RBD, and N proteins) assay.
- To determine the incidence of seroconversion following a subsequent alternative vaccine dose in the subgroup of participants that are anti-COVID-19 antibody negative following an additional homologous COVID-19 vaccine dose.
- To determine the incidence of AEs, including MAAEs, NOCMCs, and SAEs following a subsequent alternative COVID-19 vaccine dose.
- To assess whether responses to a subsequent alternative COVID-19 vaccine dose differ by type of vaccine administered.
- To assess whether responses to a subsequent alternative COVID-19 vaccine dose differ by type of cohort-defining IS medications and by disease type.

	
• To assess whether response to a subsequent alternative COVID-19 vaccine dose is associated with corticosteroid dose at the time of vaccination.• To assess whether response to a subsequent alternative COVID-19 vaccine dose is associated with clinical parameters including disease activity, co-morbid illness, age, and sex.• To determine whether disease activity is increased following a subsequent alternative COVID-19 vaccine dose, and if so, whether immunologic variables are associated with increased disease activity and/or vaccination response. 
Exploratory Objectives:
 
• To evaluate whether Baseline CD19 positive B cell numbers associate with response to an additional study COVID-19 vaccine dose in the cohort that have received B cell depletion therapy.• To evaluate the association between immune response and levels of SARS-CoV-2 antibodies at Baseline.• To evaluate the levels of Baseline interferon signal or interferon gamma-inducible protein 10 (IP-10) serum levels that associate with an effective vaccine response.• To evaluate the levels of Baseline inflammatory signals that associate with an effective vaccine immune response.• To evaluate the association between immune response to an additional study COVID-19 vaccine dose and cellular and mechanistic endpoints.
Study Design	
This is a randomized, multi-site, adaptive, open-label clinical trial comparing the immune response to different additional doses of COVID-19 vaccine in participants with autoimmune disease requiring IS medications. All study participants will have negative serologic or sub-optimal responses (defined as a Roche Elecsys® Anti-SARS-CoV-2 S result ≤ 200 U/mL) to initial COVID-19 vaccine regimen with Moderna COVID-19 Vaccine, Pfizer-BioNTech COVID-19 Vaccine, or Janssen COVID-19 Vaccine.
 
Adult Population:
 
Adult Stage 1:
 
Stage 1 of this trial will enroll up to a maximum of 900 adult study participants (up to 60 participants per arm). The trial initially focused on adults with at least 1 of 5 autoimmune diseases: systemic lupus erythematosus (SLE), rheumatoid arthritis (RA), multiple sclerosis (MS), systemic sclerosis (SSc), and pemphigus.
 
Participants will be assigned to one of 3 cohorts based on their IS regimens:
 
• Cohort A: Receipt of MMF or MPA• Cohort B: Receipt of MTX• Cohort C: Receipt of any B cell depletion therapy within the past 18 months. 
Treatment Arms: Participants in Cohorts A, B, and C will be assigned to receive an additional dose of the same vaccine as their original vaccine series.
 
Participants in Cohorts A and B will be randomized into two IS medication treatment plans as follows
 
• Participants continue to take their cohort-defining IS medications without alterations in schedule and dosing.• Participants withhold their cohort-defining IS medications before and after the additional homologous vaccine dose per protocol instructions.

Schedule of Events: Visits to assess endpoints will occur at Baseline (Week 0), Week 4 ± 1 week, Week 12 ± 2 weeks, Week 24 ± 2 weeks, Week 36 ± 2 weeks, and Week 48 ± 2 weeks. A participant will be enrolled in the study for a maximum of approximately 13 months.

Adult Stage 2:

Stage 2 of this trial will include up to a maximum of 540 adult study participants (up to 60 per arm). Participants will be eligible to receive a dose of an alternative COVID-19 vaccine. Participants may have received their additional homologous vaccine dose as a Stage 1 study participant and then enter into Stage 2 (“rollover participant”), or they may have received their additional homologous dose prior to enrollment in the study (“newly recruited participant”).

Participants will be allocated to 1 of 3 cohorts based on their IS regimens:

- Cohort D: Receipt of MMF or MPA
- Cohort E: Receipt of MTX
- Cohort F: Receipt of any B cell depletion therapy within the past 18 months.

Treatment Arms: Participants in Cohorts D, E, and F will receive a dose of an alternative COVID-19 vaccine compared to their previous COVID-19 vaccine doses. Participants who previously received 3 total doses of an mRNA vaccine (Moderna COVID-19 Vaccine OR Pfizer-BioNTech COVID-19 Vaccine) will receive their choice of either the Janssen vector-based COVID 19 vaccine or the other mRNA COVID-19 vaccine, and participants who previously received 2 doses of the Janssen vector-based COVID-19 vaccine will receive the Moderna COVID-19 Vaccine.

Participants in Cohorts D and E will withhold their cohort-defining IS medications before and after the alternative vaccine dose per protocol instructions. Participants in Cohort F who are taking MMF, MPA, or MTX in addition to B cell depletion therapies (BCDTs) will withhold these medications before and after the alternative vaccine dose per protocol instructions.

Schedule of Events: Visits to assess endpoints will occur at Baseline (Week 0), Week 4 ± 1 week, Week 12 ± 2 weeks, Week 24 ± 2 weeks, Week 36 ± 2 weeks, and Week 48 ± 2 weeks. A participant who enters Stage 2 after a serologic negative or sub-optimal response to their Stage 1 vaccine dose may be on study for up to a maximum of 26 months. A participant who is newly recruited to the study for entry into Stage 2 may be on study for up to a maximum of 13 months.

Pediatric Population:

The pediatric portion of this trial will enroll up to a maximum of 900 participants (5-17 years of age) with a Roche Elecsys® Anti-SARS-CoV-2 S result ≤ 200 U/mL after receiving an initial COVID-19 vaccine regimen (up to 60 participants per arm). Vaccines will be included in this protocol as they receive EUA or approval by FDA for a given age group. Pediatric participants will have 1 of 4 autoimmune diseases: pediatric SLE, juvenile idiopathic arthritis (JIA), juvenile dermatomyositis (JDM), or pediatric-onset multiple sclerosis (POMS).

Participants will be assigned to one of 3 cohorts based on their IS regimens:

- Cohort A: Receipt of MMF or MPA
- Cohort B: Receipt of MTX
- Cohort C: Receipt of any B cell depletion therapy within the past 18 months.

Treatment Arms: Participants in Cohorts A, B, and C will be assigned to receive an additional dose of the same vaccine as their original vaccine series.

Participants in Cohorts A and B will be randomized into two IS medication treatment plans as follows:

- Participants continue to take their cohort-defining IS medications without alterations in schedule and dosing.

	
Participants withhold their cohort-defining IS medications before and after the additional homologous vaccine dose per protocol instructions. 
Schedule of Events: Visits to assess endpoints will occur at Baseline (Week 0), Week 4 ± 1 week, Week 12 ± 2 weeks, Week 24 ± 2 weeks, Week 36 ± 2 weeks, and Week 48 ± 2 weeks. A participant will be enrolled in the study for a maximum of approximately 13 months.
 
Adaptive Design:
 
An adaptive design will be employed such that cohorts and arms defined by additional vaccine doses and IS treatment plans may be added or modified based on emerging data from existing and new FDA Emergency Use Authorization (EUA) or approvals of COVID-19 vaccines:
 
New cohorts may be defined based on changes in the medication groups if it becomes obvious that certain medications are highly associated with sub-optimal serologic response to initial COVID-19 vaccine regimen.Cohorts may limit or expand the autoimmune diseases that are eligible to be included in the clinical trial, and may include expansion cohorts of underrepresented diseases.New cohorts may include participants whose antibody response falls to sub-optimal levels over time.Based upon timing of the FDA EUA authorization for children of each of the COVID-19 vaccines used in this trial, the age range of the inclusion criteria may be expanded.Allocation or randomization to treatment with new vaccines designed for COVID variants or with a protein-based vaccine may be incorporated into the design when the products become available.Identification of additional strategies to enhance vaccine responsiveness in autoimmune diseases, including a temporary switch of immunomodulatory medications.
Primary Endpoint	The primary endpoint in the adult and pediatric populations of a protective antibody response at Week 4 will be assessed by the NIAID-VRC MSD 3 plex (Wu-1 full-length spike, RBD, and N proteins) assay.
Secondary and Exploratory Endpoints	
Secondary Endpoints
 
Secondary endpoints related to antibody response will primarily be assessed by the NIAID-VRC MSD 3 plex (Wu-1 full-length spike, RBD, and N proteins) assay; where applicable, they will also be assessed by the Roche Elecsys® Anti-SARS-CoV-2 S electrochemiluminescence immunoassay.
 
The secondary endpoints are applicable to both the adult and pediatric populations.
 
Seroconversion at Week 4 following additional doses of COVID-19 vaccine in the subgroup of participants that are anti-COVID-19 antibody negative at Week 0.

The National Institute of Allergy and Infectious Diseases (NIAID)
Statistical Analysis Plan - Protocol ACV01

- Fold increase in anti-COVID-19 antibody levels at Week 4 following an additional dose of COVID-19 vaccine in the subgroup of participants who are anti-COVID-19 antibody positive at Week 0.
- Longitudinal changes in anti-COVID-19 antibody responses from Week 0 to Weeks 4, 12, 24, 36, and 48.
- Longitudinal changes in neutralization and pseudo neutralization assays from Week 0 to Weeks 4, 12, 24, 36, and 48.
- Changes in disease activity after receipt of additional doses of COVID-19 vaccine as measured by the Clinical Global Impression of Change (CGI-C).
- Changes in disease activity after receipt of additional doses of COVID-19 vaccine as measured by the Physician Global Assessment (PGA).
- Changes in disease activity after receipt of additional doses of COVID-19 vaccine as measured by the following disease-specific assessments:
 - Adult population disease assessments:
 - Hybrid Systemic Lupus Erythematosus Disease Activity Index (H-SLEDAI) and Thanou modified Safety of Estrogens in Lupus Erythematosus: National Assessment– Systemic Lupus Erythematosus Disease Activity Index (SELENA-SLEDAI) Flare Index for SLE
 - Disease Activity Score 28 using C-reactive protein (DAS28-CRP) for RA
 - Flare assessment for SSc (including patient reported flare assessment)
 - Pemphigus Disease Area Index (PDAI) for pemphigus
 - Physician-assessed relapse for MS
 - Pediatric population disease assessments:
 - JIA:
 - JADAS10 for polyarthritis, enthesitis related to JIA, oligoarthritis, and psoriatic arthritis
 - Psoriasis Area and Severity Index (PASI) for psoriatic arthritis
 - SLEDAI-2K and Childhood-onset SLE Criteria for Global Flare [1] for pediatric SLE
